Proportions of patients with clinically important GI bleeding: proportion of patients with one or more episodes of clinically important GI bleeding as defined above

Proportion of patients with one or more infectious adverse events: proportion of patients with one or more episodes of pneumonia or CDI

1-year mortality: landmark mortality 1 year post-randomisation

Duration of life support in the ICU: the number of days alive and free from respiratory or circulatory support and of renal replacement therapy as defined below. The outcome will be days alive without use of mechanical ventilation, circulatory support or renal replacement therapy in the 90-day period, and will be defined as the percentage of days without mechanical ventilation, circulatory support and renal replacement therapy (as defined in daily collected variables) in the 90 days after randomisation

Serious adverse reactions: number of serious adverse reactions as defined below

The elements of all composite outcomes will be reported in the supplementary material

A health economic analysis will be performed. The analytic details will be based on the result of the trial and specified (cost-benefit vs cost-minimisation analyses).

Definitions of serious adverse reactions

A serious adverse reaction (SAR) is defined as any adverse reaction that results in death, is life-threatening, requires hospitalization or prolongation of existing hospitalization, or results in persistent or significant disability or incapacity.

Patients will be monitored for onset of SARs occurring between the first dose of trial medication and until discharge from the ICU. If a patient is withdrawn from the trial intervention, SARs will be recorded for 24 hours after the last dose of trial medication or discharge from ICU. If the patient is readmitted to the ICU and trial intervention is reintroduced, data collection for SARs will be resumed. If a patient experiences a SAR the patient will be withdrawn from the trial intervention but data collection and follow-up will be continued (see section 4.3.2)

SARs will be defined as follows:

Anaphylactic reactions defined as urticaria and at least one of the following

- Worsened circulation (>20% decrease in blood pressure or >20% increase in vasopressor dose)
- Increased airway resistance (>20% increase in the peak pressure on the ventilation)
- Clinical stridor or bronchospasm
- Subsequent treatment with bronchodilators

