Because of the widespread use of SUP, no reliable control group for sample size estimation is available and producing reliable sample size estimations according to anticipated effects on GI bleeding is difficult.¹ As a consequence it has been necessary to calculate sample size estimations given that something may change if we withhold PPI until GI bleeding actually happens. Assuming a baseline 90-day mortality of 25%,² $\alpha=0.05$ (two-sided), and $\beta=0.1$, 3350 patients (2 x 1675) will be needed to show a 20% relative risk reduction (RRR) or increase (RRI) corresponding to a 5% absolute risk reduction or increase in the primary outcome measure. Trial Sequential Analysis^{22,23} of existing trials (n=16) has showed that 35% (1584 patients) of the required information size to

detect or reject a 20% RRR or RRI corresponding to 4575 patients has been accrued.⁸

Consequently, there is at least an information gap of around 3000 patients taking a 20% RRR in mortality as a clinically relevant effect size.

Outcome measures

Primary outcome

The primary outcome measure is all-cause mortality within 90 days after randomisation.

Secondary outcomes

1. Proportion of patients with one or more episodes of clinically important GI bleeding, pneumonia, *Clostridium difficile* infection or myocardial ischemia. The events are defined in appendix 1
2. Proportion of patients with one or more episodes of clinically important GI bleeding
3. Proportion of patients with one or more infectious adverse events (pneumonia or *Clostridium difficile* infections)
4. All-cause mortality within 1 year after randomisation
5. Percentage of days alive without use of life support (mechanical ventilation, circulatory support or renal replacement therapy) in the 90-day period
6. The number of patients with one or more serious adverse reactions (SARs) (defined in appendix 2)
7. A health economic analysis will be performed. The analytic details will be based on the result of the trial and specified prior to the analysis.

Pre-planned subgroup analyses

The primary outcome measure will be compared in the following pre-specified subgroups (definitions provided in appendix 2)

1. Shock at randomisation (y/n) (a hypothesised increased intervention effect in patients with shock at randomisation)
2. Mechanical ventilation at randomisation (y/n) (a hypothesised increased intervention effect in patients mechanically ventilated at randomisation)

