If multiple imputation is used, the primary result of the trial will be based on these data. A 'best-worst, worst-best case' scenario will be used as a sensitivity analysis to assess the potential impact of any pattern of missingness including that the data are missing not at random (MNAR criterion) for the trial results. In the 'best-worst-case' scenario it is assumed that all patients lost to follow-up in the experimental group have had a beneficial outcome (e.g. have survived) and all those with missing outcomes in the control group have had a harmful outcome (e.g. have not survived). Conversely, in the 'worst-best-case' scenario, it is assumed that all patients who were lost to follow up in the experimental group have had a harmful outcome; and that all those lost to follow-up in the control group have had a beneficial outcome.

The unadjusted, non-imputed analysis will also be presented.

General analytic principles

1. All main analyses will compare the two intervention groups in the intention-to-treat (ITT) population.²⁴⁻²⁶

The ITT population will be all patients randomised except:

- patients withdrawing consent for the use of data
- patients who were erroneously randomised AND who did not receive the trial intervention.²⁷

The conclusion of the trial will be based on the ITT analysis

2. In all analyses, a maximum level of 5% (two-sided) type 1 error will be regarded as statistically significant
3. Test-of-interaction will be applied for all subgroup analyses (logistic regression)

Statistical analyses

Trial profile

The flow of trial participants will be displayed in a Consolidated Standards of Reporting Trials (CONSORT) diagram. The number of participants fulfilling the inclusion criteria, the number of excluded participants and reasons for exclusion, and the number of participants included in the final analyses will be presented.

Primary outcome measure

The primary analysis will be a logistic regression analysis adjusted for stratification variables (site and presence of haematological cancer, y/n) of the ITT population. Results will be presented as odds ratios and relative risk ratios (relative risk ratios computed from odds ratios with covariates set to mean values for numeric covariates and the largest group for categorical).

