The secondary analysis will be a multiple logistic regression analysis of the ITT population adjusted for stratification variables and additionally differences in potential confounders: age, SOFA score at baseline, and type of admission (medical, elective surgery or emergency surgery). Intervention group and the stratification variable haematological cancer are regarded as fixed effects and trial site is regarded as random effects in the model. Furthermore, frequencies and percentages per group will be reported and an unadjusted Chi-square test for differences in the primary outcome will be provided.

Pre-defined subgroup analyses (see former section) of the ITT population will be conducted using logistic regression analysis adjusted for stratification variables.

A sensitivity analysis of the primary outcome measure including the per-protocol population will be conducted. The per-protocol population will be all randomised patients except those having one or more protocol violations defined as:

- Patients who did not receive the allocated trial intervention at all
- Patients who did not receive the trial intervention for at least two days in a row
- Patients who received treatment (open label) with PPI or histamine-2-receptor antagonists except for those receiving it according to the protocol (i.e. occurrence of GI bleeding after randomisation).
- Patients who withdrew from trial intervention, but consented to the use of data
- Monitoring revealed that one or more in- or exclusion criteria were violated

Secondary outcome measures

The secondary outcomes will only be analysed in the ITT population. The primary analysis of the binary secondary outcome measures will be a logistic regression analysis adjusted for the stratification variables (site and presence of haematological cancer). Results will be presented as odds ratios and relative risk ratios.

Furthermore, frequencies and percentages per group will be reported and an unadjusted Chi-square test for differences in the primary outcome will be provided.

The primary analysis of rate data ('Percentage of days alive without life support in the 90-day period') will be a generalized linear model (initially Poisson distribution, alternatively negative binomial).²⁸ If the assumptions for Poisson distribution or negative binomial distribution are not met, data will be analysed using the non-parametric Van Elteren test adjusted for site, but no other variables.²⁹

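### The percentage of days free of life support is assigned count models that do not suit a bounded percentage, with no stated rule for leaving them for the rank test

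*Combined protocol and SAP*

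**What the plan says.** The SAP lists as its fifth secondary outcome "Percentage of days alive without use of life support (mechanical ventilation, circulatory support or renal replacement therapy) in the 90-day period". Protocol Appendix 4 agrees that it is a percentage: it "will be defined as the percentage of days without mechanical ventilation, circulatory support and renal replacement therapy" over the 90 days after randomisation. Neither text spells out how days after death enter.

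Under Secondary outcome measures, the SAP calls this rate data and says the primary analysis "will be a generalized linear model (initially Poisson distribution, alternatively negative binomial". The next sentence gives the exit: "If the assumptions for Poisson distribution or negative binomial distribution are not met, data will be analysed using the non-parametric Van Elteren test". That test is adjusted for site only.

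The SAP gives no test or threshold for deciding that assumptions are not met. It does not say whether one model or both must fail. It names no standard error type, offset or denominator. On significance it says: "In all analyses, a maximum level of 5% (two-sided) type 1 error will be regarded as statistically significant".

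**The concern.** The outcome lies between 0 and 100. In an ICU population one expects a cluster at or near 0 (patients who die on support) and a large group near the top (survivors with short support). Poisson requires the variance to equal the mean. Negative binomial allows extra variance, but in a right-skewed form with no upper limit. Neither describes such data, and their standard errors go wrong in opposite directions: Poisson's are too small and negative binomial's too large.

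The exit is undefined. Negative binomial is the usual remedy for overdispersion, so an analyst who checks only overdispersion would stop there, at the model with little power. If the exit is taken, the Van Elteren test gives a p-value but no effect estimate.

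This outcome carries safety weight. Protocol section 8.3.1 does not record serious adverse events as an entity, partly because the most important ones are expected to show in days alive without life support. Appendix 6 relies on the same outcome for serious renal consequences. An underpowered model could miss harm, and an anticonservative one could suggest harm or benefit that is not there.

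**Working it through.** **The plan's own figure.** The documents state no mean, SD, target difference or power for this outcome. The only figure to reproduce is the trial size ("3350 patients (2 x 1675) will be needed to show a 20% relative risk reduction (RRR"), which supplies N and mortality. For 25% against 30%, two-sided 5%, 90% power:

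n = [1.960 × √(2 × 0.275 × 0.725) + 1.2816 × √(0.25 × 0.75 + 0.30 × 0.70)]² / 0.05² = (1.238 + 0.808)² / 0.0025 ≈ 1674 per arm, against 1675 stated.

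**Inputs.** From the documents: 1675 per arm, 25% mortality, a 5-point shift either way, two-sided 5%. Assumed, because the documents give nothing: lognormal support days (median 4 or 8, sigma 1), exponential death times (median day 8 to 15), and 30-80% of those who die being on support until death. This puts 12-22% of patients at zero and the main peak at about 84-88 days.

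**Poisson by hand.** With model-based standard errors, type I error = 2 × [1 − Φ(1.96 / √(variance/mean))]. Take two groups only, 75% survivors and 25% dead, with no spread within either:

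- Survivors 92%, dead 10%: mean 0.75 × 92 + 0.25 × 10 = 71.5; variance 0.75 × 0.25 × 82² = 1261; ratio 17.6; type I error 64%.
- Survivors 92%, dead 40%: mean 79; variance 507; ratio 6.4; type I error 44%.
- Survivors 90%, dead 50%: mean 80; variance 300; ratio 3.75; type I error 31%.

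Spread within the groups raises each figure. The Poisson result also depends on units: rescaling 90 days to 100% multiplies variance/mean by 100/90 = 1.11 with no change in the data.

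**Negative binomial by hand.** In scenario B (median 4 support days, 80% of the dead on support) the mean is 62.7 days, the SD 36.2 and the fitted dispersion 1.85. The model's implied SD is √(62.7 + 1.85 × 62.7²) = 85.6, which is 2.37 times the true SD. The test therefore needs a true z of 1.96 × 2.37 = 4.64, so its real size is essentially zero.

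**Simulation.** 300-600 trials per cell, no site effects, with a Wilcoxon test standing in for Van Elteren. Response in percent of 90 days; scenario C is median 8 and 60%, D is median 4 and 30%:

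| Scenario | Quantity | Poisson | Neg. binomial | Log-link, robust SE | Rank test |
|---|---|---|---|---|---|
| B | Type I error | 67.5% | 0% | 4.3% | 3.8% |
| B | Power, 25→30% | – | 4.5% | 88.0% | 70.7% |
| C | Type I error | 64.7% | 0% | 4.0% | 4.8% |
| C | Power, 25→30% | – | 8.8% | 84.8% | 68.3% |
| D | Type I error | 62.3% | 0% | 4.5% | 6.7% |
| D | Power, 25→30% | – | 20.2% | 84.3% | 68.2% |

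Ranges over all scenarios, with power for 25→20% or 25→30%:

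- 90-day denominator, days or percent: Poisson type I error 62-71%. Power: negative binomial 5-26%, robust 84-95%, rank test 68-74%. Type I error: robust 4-7%, rank test 3-7%.
- Denominator days alive, percent as response: Poisson type I error 60-65%. Power: negative binomial 2-7%, robust 64-86%, rank test 51-69%.
- Days as response with a log(days alive) offset: Poisson type I error 10-33%.

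**Would a fit check catch it?** A chi-square goodness-of-fit check on 3350 patients rejected both Poisson and negative binomial in 100% of simulated null trials (three scenarios, 100 trials each). The fitted negative binomial put 22-25% of its mass above the 90-day maximum.

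**Leaving out haematological cancer.** A further simulation used 40 sites (the SAP has 31, with 5-10 more expected), stratified blocks, cancer prevalence of 3% or 8% with 50% mortality in those patients, 60% of deaths on support, median 5 support days, and 600 trials per cell. Van Elteren by site alone had type I error 4.8% and 4.5%, and power 65.5% and 63.3% for 25→30%. By site and cancer: 5.0% and 3.8%, and 66.5% and 61.5%. The simulation standard errors are about √(0.05 × 0.95 / 600) = 0.9 points and √(0.65 × 0.35 / 600) = 1.9 points, so no difference is detectable.

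**The case against.** The strongest reply is that the next sentence of the SAP already deals with this. If the data cannot meet the count-model assumptions, the written plan leads to Van Elteren, and the fit check above shows that any real inspection would get there. This stands, and it limits the finding: the poor error rates describe an analyst who keeps a count-model result. It does not remove the gap, because the SAP requires no such check. If the exit is always taken, the first two steps serve no purpose.

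Second, the shape of the data and all the rates are assumed. The SAP speaks of rate data; with a days-alive offset the Poisson type I error is 10-33%, and negative binomial power reached 26% where fewer patients were at zero. This stands too, which is why ranges are given. Even 10-33% is two to seven times the 5% limit.

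Third, the analysis is done with groups coded X and Y, so the model cannot be chosen to favour a known arm. That is true, but blinding does not correct a model's error rate. The SAP also cites a methods paper on count data at this step. It may describe a model check, but the SAP text does not.

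Fourth, the count-model framework need not be abandoned: a log-link model with robust standard errors held its size, gave an effect estimate and was more powerful than the rank test for a mortality-driven shift. This stands and is reflected in the fix.

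**Conclusion.** The first-line models do not suit a percentage bounded at 100, and the exit from them has no criterion. If a count-model result is kept, type I error is about 10-70% for Poisson with model-based standard errors. For negative binomial it is about 0%, with 2-26% power for a 5-point mortality shift. These sizes depend on the assumed two-peaked data and on the denominator; the direction of both errors was the same in every scenario tried.

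A reader might infer more, but the documents do not support it:

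- That the trial will report mostly false positives, or a test with almost no power, for this outcome. The fallback is written down, and following it properly gives a rank test of about correct size.
- That omitting haematological cancer from the fallback damages it. It departs from the randomisation strata, but no measurable loss was found.
- That the trial's main conclusion is at risk. This is one of seven secondary outcomes; the mortality analysis and N = 3350 are untouched.

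The change is worth making because it removes an undefined judgement and supplies an effect estimate.

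**What to change.** - Remove Poisson and negative binomial models with model-based standard errors as the first-line analysis.
- Make the already named Van Elteren test, stratified by site, primary from the start. Adding haematological cancer would match the randomisation but is optional.
- Report the difference in means with a bootstrap 95% CI as the effect estimate.
- An acceptable alternative is a log-link model with robust standard errors. Choose one now and name it.
- State the denominator as 90 days and how days after death count.

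The cost is SAP wording, with no new data. The downside is that the rank test can have less power than a robust comparison of means (68-74% against 84-95% in the 90-day scenarios) and gives no effect estimate by itself, which is why the bootstrap interval is needed.
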